- Scenario 2: the patient must have received an aromatase inhibitor (letrozole, arimidex, exemestane) or tamoxifen or fulvestrant plus palbociclib as standard of care **or** received a CDK4/6 inhibitor (palbociclib or ribociclib or abemaciclib), **and** demonstrated evidence of disease progression. If the patient was enrolled in a randomized clinical trial involving ribociclib or abemaciclib or palbociclib (such as the MONALEESA or PALOMA series of trials), then it **must** be known after study discontinuation and unblinding that the patient received the investigational drug and not placebo. Ribociclib or abemaciclib or palbociclib can also be given as standard of care. Documentation of progression and duration of response on aromatase inhibitor or tamoxifen plus CDK 4/6 inhibitor should be provided whenever possible. If patient received prior fulvestrant, exemestane must be the hormone therapy backbone in the randomization. If patient received prior exemestane, fulvestrant

must be the hormone therapy backbone in the randomization. If neither has been administered, selection of fulvestrant or exemestane in the randomization will be per investigator discretion.

- Adequate baseline laboratory studies (hematologic and chemistry), including the following parameters:
 - Absolute neutrophil count ≥ 1500 per microliter, Platelets $\geq 75,000$ per microliter, Hemoglobin level ≥ 8.0 gm/dL on screening complete blood count
 - Potassium and total calcium (corrected only in the case of hypoalbuminemia) within normal limits of the local laboratory (Screening values can be rechecked after electrolyte repletion and before the first dose of study medication, if necessary.)
 - Serum creatinine level ≤ 1.5 mg/dL **or** estimated glomerular filtration rate ≥ 50 mL/min.
 - In absence of liver metastases, alanine aminotransferase (ALT) and aspartate aminotransferase (AST) should be below $2.5 \times$ the upper limit of normal (ULN). If the patient has liver metastases, ALT and AST should be $< 5 \times$ ULN.
 - Total bilirubin $\leq 1.5 \times$ ULN. (In patients with well documented Gilbert's Syndrome, total bilirubin $\leq 3 \times$ ULN with direct bilirubin within normal range.)
 - INR ≤ 1.5
- (a) Written informed consent and HIPAA authorization obtained from the subject/legal representative prior to performing any protocol-related procedures;

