(b) Subjects must be willing and able to comply with scheduled visits, treatment schedule, laboratory testing, and other requirements of the study
- Must be able to swallow ribociclib and oral aromatase inhibitor, such as letrozole or exemestane.

3.2 Exclusion Criteria:

A subject **who meets any of the following criteria is ineligible** for the study:

1. Patient has a known hypersensitivity to any of the excipients of ribociclib, aromatase inhibitors (such as letrozole) or fulvestrant.
2. **Active** central nervous system (CNS) disease. History of CNS metastases or cord compression is allowable if the patient has been clinically stable for at least 4 weeks since completion of definitive treatment and is off systemic steroids. In the case of brain metastases, the patient must have stable or improved imaging at least 4 weeks after completion of definitive treatment. If there is evidence of active leptomeningeal disease, the patient is ineligible.
3. Identified as having visceral crisis, lymphangitic spread, or leptomeningeal carcinomatosis. Visceral crisis is not the mere presence of visceral metastases but implies severe organ dysfunction as assessed by symptoms and signs, laboratory studies, and rapid progression of the disease.
4. Received more than 1 prior systemic chemotherapy in the unresectable or metastatic setting. If the patient received 1 prior systemic chemotherapy, the patient is eligible. Having received prior therapies for breast cancer (such as everolimus or experimental agents) does not affect eligibility for this study.
5. Completion of major surgery, chemotherapy, targeted therapy (such as everolimus or experimental agents) or radiation within 14 days prior to starting investigational drug **or** has not recovered from major side effects. There is no required washout period from completion of prior anti-estrogen therapy (either scenario) or prior CDK 4/6 inhibitor (if scenario 2) to initiation of ribociclib/placebo and anti-estrogen on trial.

6. Residual acute toxic effects of prior anti-cancer therapy that have not resolved to CTCAE v.4 Grade \leq 1. Exception to this criterion: patients with grade 1 taxane-induced neuropathy, any grade of alopecia, amenorrhea or other toxicities not considered a safety risk for the patient as per investigator's discretion, are allowed to enter the study.

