7. Presence of a concurrent malignancy or malignancy diagnosed within 5 years of randomization, with the exception of basal or squamous cell carcinoma, non-melanomatous skin cancer, curatively resected cervical cancer, localized prostate cancer treated with curative intent, and stage I colorectal cancer treated with curative resection.
8. Patient has impairment of gastrointestinal (GI) function or GI disease that may significantly alter the absorption of the study drugs (e.g. ulcerative diseases, uncontrolled nausea, vomiting, diarrhea, malabsorption syndrome, or small bowel resection).
9. Patient has a known history of HIV infection (testing not mandatory)
10. Clinically significant, uncontrolled heart disease and/or cardiac repolarization abnormality including any of the following:
 - History of myocardial infarction (MI), angina pectoris, symptomatic pericarditis, or coronary artery bypass graft (CABG) within 6 months prior to study entry
 - Documented cardiomyopathy
 - Patient has a known Left Ventricular Fraction (LVEF) $<50\%$ as determined by Multiple Gated acquisition (MUGA) scan or echocardiogram (ECHO).
 - Long QT syndrome or family history of long QT syndrome or family history of idiopathic sudden death or congenital long QT syndrome, or any of the following:
 - i. Risk factors for Torsades de Pointe (TdP) including uncorrected hypocalcemia, hypokalemia or hypomagnesaemia, history of cardiac failure, or history of clinically significant/symptomatic bradycardia
 - ii. Concomitant medications(s) with a known risk to prolong the QT interval and/or known to cause Torsades de Pointe that cannot be discontinued or replaced by safe alternative medication (e.g. within 5 half-lives or 7 days prior to starting study drug)
 - iii. Inability to determine the QTc interval
 - Clinically significant cardiac arrhythmias (e.g., ventricular tachycardia), complete left bundle branch block, high-grade AV block (e.g., bifascicular block, Mobitz type II and third degree AV block)
 - Systolic Blood Pressure (SPB) >160 or <90 mmHg
11. Corrected QT interval (QTcF) > 450 msec (QT interval using Fridericia's correction) on screening electrocardiogram. If QTc prolongation is felt to be related to electrolyte imbalance, an EKG can be repeated after correction of electrolytes. Mean resting heart rate 50-100 bpm (determined from ECG).

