- Assessing cardiovascular dysfunction or impaired liver oxygenation, including hypotension or right heart failure as possible etiologies for liver dysfunction.
- Liver biopsy as clinically indicated to assess pathological change and degree of potential liver injury

Dose modification for QTc prolongation:

Grade	DOSE ADJUSTMENT / MANAGEMENT REC'S
For All Grades	
 • Check the quality of the ECG and the QT value and repeat if needed • Perform analysis of serum electrolytes (K⁺, Ca⁺⁺, Phos, Mg⁺⁺). If outside of the normal range, interrupt ribociclib administration, correct with supplements or appropriate therapy as soon as possible, and repeat electrolytes until documented as normal. • Review concomitant medication usage for the potential to inhibit CYP3A4 and/or to prolong the QT interval. • Check compliance with correct dose and administration of ribociclib.
Grade 1: QTc 450-480 ms	
 • No dose adjustment required.
Grade 2: QTc 481-500 ms	
 • Interrupt ribociclib • Perform a repeat ECG one hour after the first QTc of ≥ 481ms • If QTcF prolongation resolves to < 481 ms, resume treatment at the next lower dose level; • • If QTcF ≥ 481 ms recurs, interrupt dose until QTcF resolves to < 481 ms; then resume KISQALI at next lower dose level. • Repeat ECGs 7 days and 14 days after dose resumption (then as clinically indicated) for any patient who has therapy interrupted due to QTc ≥ 481 ms
Grade 3: QTc ≥ 501 ms on at least two separate EKGs.	
 • Interrupt ribociclib/placebo. • Consider consulting a local cardiologist • Interrupt KISQALI treatment if QTcF greater than 500 ms • Perform a repeat ECG within one hour of the first QTcF of ≥ 501ms • If QTcF remains ≥ 501ms, consult with a cardiologist (or qualified specialist) and repeat cardiac monitoring as indicated until the QTcF returns to < 481ms • If QTcF prolongation resolves to < 481 ms, resume treatment at the next lower dose level. • If QTcF remains ≥ 481 ms after performing steps 1-4 as directed in “For All Grades”, discontinue ribociclib • After resumption, EKG should be repeated 7 days and 14 days and then at least monthly. If stable at least monthly for 3 months, then can have EKG every 3 months.

	
 If QTc > 501 ms recurs, discontinue ribociclib/placebo

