		^A Exceptions to the +/- 4 days are CT C/A/P + bone scan (OR PET) which should be performed within 28 days of trial registration and after every third cycle of treatment (within 14 days of day 1 of each third cycle – ideally within 7 days of day 1) and tissue biopsy (+/- 7 days).						
		^B Every 4 weeks. Day 1 visits for each cycle should occur at 28±4 days from day 1 of the previous cycle. Blood draws on that day should also fall within this +/- 4 day window. Exceptions to the +/- 4 days are CT C/A/P + bone scan (OR PET) as described above. The +/- 4 day window includes C1D15.						
		^C Ribociclib (or placebo) will be supplied per study. On D1 of every cycle prior to drug dispensation and dose administration, subject's disease status/non-progression will be confirmed by the treating investigator, including clinical and radiographic assessment. RECIST restaging will be confirmed for the most recent scans received, including documentation of investigator sign off on calculation of percentage change from baseline and nadir and overall response, prior to treatment. If the new scan information becomes available mid cycle, the study team will inform the subject if treatment discontinuation is required per protocol in real time, and document date of treatment discontinuation.						
		^D Serum Pregnancy test (women of childbearing potential)						
		^E Albumin, alkaline phosphatase, total bilirubin, bicarbonate, BUN, calcium, chloride, creatinine, glucose, potassium, total protein, SGOT [AST], SGPT [ALT], sodium.						
		^F EKG will be performed at baseline, C1D15, C2, and Cycle 4. If grade 3 or 4 QTC prolongation occurs, see section 7.3 for monitoring/dose modification. If no EKG abnormalities, additional EKGs are not required for cycles after C4a or C4b, except						

		Progression.
		^G Scans should be performed within 28 days of study registration, prior to every third cycle of treatment (i.e, preferably within 7 days of Cycle 4a day 1, Cycle 7a day 1, Cycle 10a day 1, and so on, but allowance for up to within 14 days of the next treatment cycle). Corresponding RECIST restaging will be conducted in real time following scans and signed (electronically or wet ink) by the investigator, including confirmation of overall disease status per RECIST v.1.1.1.

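### Exclusion 11 lists the normal resting heart-rate range as if it disqualified; secondarily, exclusion 10 names low magnesium, which no scheduled screening test measures

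*Combined protocol and SAP*

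**What the plan says.** Section 3.2 opens by stating that a subject "who meets any of the following criteria is ineligible", so each numbered item is a reason to refuse entry. Item 11 sets a QTcF limit of more than 450 msec, allows a repeat ECG after electrolytes are corrected, and closes with "Mean resting heart rate 50-100 bpm (determined from ECG". The last bullet of item 10, directly above, reads "Systolic Blood Pressure (SPB) >160 or <90 mmHg".

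Item 10 also lists risk factors for Torsades de Pointes. These include "uncorrected hypocalcemia, hypokalemia or hypomagnesaemia" and a "history of clinically significant/symptomatic bradycardia".

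On electrolytes, the baseline laboratory criterion in section 3.1 asks for "Potassium and total calcium (corrected only in the case of hypoalbuminemia) within normal limits of the local laboratory". The chemistry panel in section 10.2 (Table 2, footnote E) begins "Albumin, alkaline phosphatase, total bilirubin, bicarbonate, BUN, calcium, chloride, creatinine, glucose, potassium, total protein" and continues with AST, ALT and sodium. Section 10.1 (Table 1, footnote F) gives the same list for Scenario 1. Section 11.2.1 refers only to serum chemistry in general terms. Magnesium testing appears in one place, the QTc table of section 7.3, where the instruction for all grades is to "Perform analysis of serum electrolytes", and magnesium is among those named.

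**The concern.** Items 10 and 11 are the entry screen for arrhythmia risk on a drug known to prolong QT; section 8.1 reports that QTc prolongation was the dose-limiting toxicity in phase I. A criterion in that screen should be correct as printed. The heart-rate line gives an acceptable range in a list of unacceptable findings, with no word such as *outside* or *not* to turn it round. Followed literally, it rejects the patients it should accept and lets through the rates it should catch.

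The magnesium point is of a different kind. That criterion is worded correctly, but the protocol schedules no test that would supply the value. A site that runs only the listed tests has nothing on file to show that the criterion was checked.

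**Working it through.** No arithmetic applies, and the plan gives no figure to reproduce. The check is to read the sections against one another.

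**Heart rate.** Apply the opening rule of section 3.2 (meeting an item means ineligible) to each numerical limit in this part of the list:

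| Item | Printed condition | Literal effect | Direction |
|---|---|---|---|
| 10, systolic pressure | above 160 or below 90 mmHg | extreme values excluded | correct |
| 11, QTcF | above 450 msec | long QTcF excluded | correct |
| 11, heart rate | 50-100 bpm | normal rates excluded, others admitted | reversed |

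On the literal reading, a patient at 72 bpm is ineligible, while patients at 45 or 110 bpm are not excluded by this line.

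The next question is whether another part of the protocol puts this right. Section 3.1 and the synopsis contain no heart-rate criterion. Item 10 excludes a history of clinically significant or symptomatic bradycardia and clinically significant arrhythmias, so those patients are still screened out. What remains uncovered, read literally, is an asymptomatic rate below 50 or above 100 bpm on the screening ECG.

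**Magnesium.** Trace the three electrolytes of item 10 through the places where a baseline value could come from:

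| Electrolyte | Section 3.1 laboratory criterion | Table 1, footnote F | Table 2, footnote E |
|---|---|---|---|
| Calcium | yes | yes | yes |
| Potassium | yes | yes | yes |
| Magnesium | no | no | no |

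Both calendars carry the same 14 analytes, so the gap is the same whichever scenario a patient enters by. The electrolyte work-up in section 7.3 belongs to the dose-modification rules for QTc prolongation. It is triggered by a finding on treatment and cannot serve as a screening test.

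Item 10 could be meant to cover only low magnesium that is already known. The wording around it suggests otherwise. The ejection-fraction bullet and the HIV item both carry the word *known*, and the HIV item adds that testing is not mandatory. The electrolyte line has no such qualifier.

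**The case against.** The best reply on heart rate is that section 3.2 mixes requirements and permissions into its exclusions throughout. Item 2 requires stable imaging after treatment of brain metastases, item 4 confirms that one prior chemotherapy is allowed, and item 16 orders a pregnancy test. Nobody treats satisfying those sentences as disqualifying, and the heart-rate fragment reads as the same kind of misplaced requirement. This largely stands as an account of intent, and sites would probably act on it. The difference is that the other sentences carry a verb that fixes their direction, and the heart-rate fragment has none. The eligibility checklist that physicians sign under section 4 is not among the documents, so whether it repeats the slip is unknown.

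A reader might go further and infer that every enrolled patient with a normal pulse is a deviation that can never be approved, because Appendix F says the monitoring committee will no longer approve deviations from eligibility criteria. The documents do not support that. Section 12.3 still describes eligibility waivers being submitted to and approved by that committee, and section 4 lists waiver approvals among the registration papers. The deviation itself also depends on the literal reading.

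On magnesium, the reply is that not every exclusion needs a scheduled test, that section 4 accepts source documents beyond those it lists, and that QTcF is screened directly by ECG. All of that is fair. A site can file a local magnesium result, so it would be wrong to infer that the criterion cannot be documented. What stands is that no scheduled test supplies the value.

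**Conclusion.** The heart-rate sentence in exclusion 11 is wrong as printed and is not corrected elsewhere. It is most likely an inclusion-type requirement in the wrong list. The missing magnesium test is a real but secondary gap. Both merit correction as matters of eligibility and safety wording.

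The lines apply to every patient screened, but the documents give no distribution of heart rate or magnesium at screening, so the number wrongly admitted or refused cannot be estimated. It would go too far to infer that unsafe patients were enrolled, because sites may have applied the intended rule and measured magnesium locally. PFS, its analysis and the power calculation are unaffected.

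The practical effect from here is small. Scenario 1 is closed to accrual. The placebo expired in August 2023, and the Scenario 2 patients then on treatment were unblinded (sections 10.3 and 13.6). The protocol does not expressly say that Scenario 2 accrual has ended; that few or no further patients will be screened is an assumption, though further blinded randomization without placebo is implausible. The printed criterion is still the text against which eligibility would be judged.

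**What to change.** Reword the last sentence of item 11 as *mean resting heart rate <50 or >100 bpm (determined from ECG)*, or move the 50-100 bpm requirement to section 3.1. Either removes the ambiguity.

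Add magnesium to the screening chemistry in the study calendar: section 10.2, footnote E, and section 10.1, footnote F, for consistency. Naming it beside potassium and calcium in section 3.1 would bring the inclusion and exclusion lists into line.

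The cost is a short wording amendment and one more analyte on blood already drawn. Visits, sample size and analysis do not change.

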4. REGISTRATION PROCEDURES

***** Please see Appendix F for Guidelines for Affiliate Institutions for Registration and Data Reporting Requirements.**

CUMC Research Participant Registration (CUMC Subjects ONLY)

Confirm eligibility as defined in Section 3.

Obtain informed consent, by following procedures defined in section entitled Informed Consent Procedures, along with applicable institutional policies and federal regulations.

Only Investigators/Research personnel properly trained and delegated to consent subjects for this protocol will participate in the consenting process. Furthermore, properly delegated/trained Physician Investigators (i.e., MD, MD PhD) are required to sign/verify a protocol specific Eligibility Checklist for each subject enrolled on the study, in addition to providing the relevant source documentation to confirm subject eligibility.

All participants must be centrally registered through the Central Registration Office within Herbert Irving Comprehensive Cancer Center at CUMC prior to initiation of study treatment.

Registration hours are available Monday through Friday from 9:00am – 5:00pm EST (excluding holidays and weekends). Same day patient registrations (and after hour registrations) will be accommodated on a case-by-case basis provided that the study team has expressed all time sensitive registration concerns/cases in a timely manner to the Central Registration Office.

CPDM Central Registration Procedures:

Within 48 hours of obtaining consent (excluding holidays and weekends), a completed/signed IRB approved informed consent HIPAA form, and demographics forms must be submitted to the CPDM Central Registration Office via an email to [contact] or fax to [contact], with the subject line “[**PROTOCOL# AAAP9506 Pending Subject Registration Request (PHI)**”. Upon receipt, applicable subject information as well as a “pending eligibility” status will be entered into HICCC’s

institutional database. This status will remain until further source documentation is made available to confirm overall patient eligibility. Required materials for all pending registration submissions are as follows:

- Completed/signed IRB approved/stamped Informed Consent Forms, including additional study ICFs (i.e. tissue, DNA, etc.) as applicable
- The completed/signed IRB approved HIPAA Authorization form
- Completed/signed CPDM ICF checklist
- Completed/signed HICCC personal census form
- Completed/signed CPDM Demographics Note to File

In order to confirm eligibility status, Investigators/designees (i.e., study specific Clinical Research Coordinator/Research Nurse, etc.) must submit the following documentation to the Central Registration Office via email or fax:

- The completed/signed study specific Eligibility Checklist (signed by a Physician level Investigator)
- Copies of source documentation necessary for each item to be verified on the CUMC specific Eligibility Checklist, including but not limited to:
 - Copy of required laboratory test and procedure reports (i.e., hematology, serum chemistry, pregnancy test when applicable, and pertinent radiology reports such as CT/bone scans, PET/CT scans, MRI reports, etc.)
 - Copy of pathology and surgical reports
 - Copy of clinic note(s) or other appropriate medical records capturing the consent process information, along with providing source documentation of any other items needed for screening/eligibility that are not captured in other source document forms (e.g., positive investigator statements of unique eligibility items not captured via other direct source documentation, concomitant medication lists, etc)
 - Protocol deviation/waiver approvals (if applicable)
- **Please note:** subject line of email or fax should include the following: “PROTOCOL# AAAP9506 Complete Subject Registration Request (PHI).”

Upon Receipt of the above-mentioned documentation, participant eligibility information will be verified by a qualified Central Registration Registrar. If any questions arise during the review process, queries in the form of emails will be addressed to the applicable study team personnel for clarification prior to enrollment. All applicable finalized registration/eligibility information will then be entered into HICCC’s institutional database by the Central Registration Registrar. Upon completion, an official subject registration notification email will be sent to the PI/research team, which will include eligibility/enrollment status, as well as subject ID information. Protocol therapy may not be initiated prior to receipt of this notification from the Central Registration Office.

All screen fail/ineligible subjects, as well as subjects who withdraw consent prior to enrollment/initiation of protocol therapy must be submitted to the Central Registration office in a manner analogous to the procedures noted above. Applicable source documentation will be required within the corresponding submissions.

